4.0 TREATMENT PLAN

4.1 Treatment Dosage and Administration

Pediatric Radiation Oncology with Movie Induced Sedation Effect (PROMISE) is an interactive, incentive-based movie system that integrates with a video surveillance gating module (VisionRT) to help keep a children's attention and prevent him or her from moving during radiation treatment. This technology is being studied as an alternative sedation solution for pediatric patients needing radiation treatment.

All patients on study will receive radiation treatment per standard of care for patient's diagnosis. The dose, fractionation, and possible concurrent treatments will all vary from patient to patient. Because we plan to enroll such a wide variety of patients, treatment will be unique for every patient. PROMISE will be consistent throughout the study, though, and attempted in every patient that can tolerate it.

The following protocol will be used to implement PROMISE for each patient:

- 1) Consultation:
 - During initial consultation with eligible patients, the clinical trial will be discussed and should they agree to participate, patients/families will be consented.
- 2) CT simulation session:
 - Initial screening for PROMISE will occur in CT simulation suite.
 - Patient will be instructed to be NPO for 6 hours, and anesthesia will be available as stand-by.
 - CT scan of region of interest, per standard clinical practice, will be attempted with modified version of PROMISE for audiovisual distraction, with patient under direct observation.
 - If the patient cannot comply with instructions of laying still for a few minutes for the CT scan, the attending radiation oncologist will be asked to re-evaluate the appropriateness of evaluating the child with PROMISE.
 - If PROMISE ultimately is unsuccessful, the patient will undergo general anesthesia for the CT simulation and subsequent treatments.
- 3) Treatment sessions:
 - For the first treatment, a 60-minute slot will be scheduled. Patient will be instructed to be kept NPO for 6 hours and anesthesia will be available on stand-by. Patient will be immobilized with PROMISE, and treatment will be attempted.
 - If patient successfully completes treatment with PROMISE, future treatments will be scheduled in 30-minute slots without anesthesia available on standby.
 - If patient cannot successfully complete PROMISE, second treatment will be scheduled and planned similar to the first treatment, in a 60-minute slot with patient NPO and anesthesia on standby.
 - If second treatment is also not successful, no more attempts will be made with PROMISE and remaining treatments will be done under general anesthesia.
 - If the second treatment is successful, third treatment will be performed similarly.
 - If third treatment is successful, remaining treatments will be with PROMISE only, in 30-minute slots without anesthesia on standby.

- If third treatment is not successful, no more attempts will be made with PROMISE and remaining treatments will be done under general anesthesia.
- For each treatment session, the following workflow data will be measured: 1) total treatment time, 2) average patient movement (VisionRT), 3) number of beam turn offs due to movement beyond threshold (VisionRT).

4.2 Toxicities and Dosing Delays/Dose Modifications

There are no known or expected toxicities associated with PROMISE. The only toxicity that could be indirectly associated with PROMISE is if the child moves during radiation treatment and this results in radiation temporarily being delivered to the wrong target. However, PROMISE is integrated with the video surveillance gating module VisionRT, so that if the patient moves beyond predefined safety threshold, the beam will automatically stop, so this is not an event that would ever be expected to happen. This auto-beam off ability is a unique feature of PROMISE that is not seen in competing technologies.

4.3 Concomitant Medications/Treatments

N/A. Radiation and any other concomitant medications/treatments will be done as per standard of care. If patient cannot do PROMISE, general anesthesia will be used for each radiation treatment as per standard of care.

4.4 Duration of Therapy

In the absence of treatment delays due to adverse events, treatment (PROMISE) may continue for **duration of radiation treatment course** or until any of the following that may necessitate stopping radiation treatment:

- Disease progression
- Inter-current illness that prevents further administration of treatment
- Unacceptable adverse event(s)
- Subject's parent or guardian decides to withdraw subject from the study, **OR**
- General or specific changes in the patient's condition render the subject unacceptable for further treatment in the judgment of the investigator.

4.5 Duration of Follow Up

Follow up will occur 30 days (+/- 14 days) after treatment termination.

4.6 Removal of Subjects from Protocol Therapy

Subjects will be removed from therapy when any of the criteria listed in [Section 5.5](#) apply. Notify the Principal Investigator, and document the reason for treatment discontinuation and the date of discontinuation. The subject should be followed-up per protocol.

5.0 STUDY PROCEDURES

5.1 Screening/Baseline Procedures

Assessments performed exclusively to determine eligibility for this study will be done only after obtaining informed consent. Assessments performed for clinical indications (not exclusively to determine study eligibility) may be used for baseline values even if the studies were done before informed consent was obtained.

All screening procedures must be performed within 30 days prior to registration unless otherwise stated. The screening procedures include:

5.1.1 Informed Consent

5.1.2 Medical history

Complete medical and surgical history

5.1.3 Demographics

Age, gender, race, ethnicity

5.1.4 Review subject eligibility criteria

5.1.5 Review previous and concomitant medications

5.1.6 Physical exam including vital signs, height and weight

Vital signs (temperature, pulse, respirations, blood pressure), height, weight

5.1.7 Performance status

Performance status evaluated prior to study entry according to Appendix A (Section 12.1)

5.1.8 Quality of life (QOL) questionnaires

Baseline patient/family-reported health quality of life (QOL), assessed using PedsQL 3.0 Cancer Module, and patient/family-reported anxiety, measured by the modified Yale Preoperative Anxiety Survey Short Form (mYPAS-SF), will be assessed. The PedsQL for the patient will be optional.

5.2 Procedures During Treatment

5.2.1 Prior to Initiation of Treatment

- History, physical exam, vital signs
- PROMISE Screening
 - Initial screening for PROMISE will occur in CT simulation suite.
 - Patient will be instructed to be NPO for 6 hours, and anesthesia will be available as stand-by.
 - CT scan of region of interest, per standard clinical practice, will be attempted with modified version of PROMISE for audiovisual distraction, with patient under direct observation.
 - If the patient cannot comply with instructions of laying still for a few minutes for the CT scan, the attending radiation oncologist will be asked to re-evaluate the appropriateness of evaluating the child with PROMISE.
 - If PROMISE ultimately is unsuccessful for the CT simulation, the patient will undergo general anesthesia for the CT simulation and (at treating physician's discretion) subsequent treatments.

5.2.2 Radiation Treatment

- For the first treatment, a 60-minute slot will be scheduled. Patient will be instructed to be kept NPO for 6 hours and anesthesia will be available on stand-by. Patient will be immobilized with PROMISE, and treatment will be attempted.
 - If patient successfully completes treatment with PROMISE, future treatments will be scheduled in 30-minute slots without anesthesia available on standby

If patient cannot successfully complete PROMISE, the second treatment may be scheduled and planned similar to the first treatment at treating physician's discretion, in a 60-minute slot with patient NPO and anesthesia on standby, or patient can proceed with anesthesia for subsequent treatments. The patient may continue subsequent treatments with anesthesia at the physician's discretion..

- At the treating physicians discretion, the same procedures undertaken on Day 1 may be attempted a week later (+/- 7 days) if PROMISE was previously unsuccessful. By this time, many patients will potentially be calmer and more accustomed to treatment, a new environment, etc. and more likely to tolerate PROMISE.

5.2.3 At Each Treatment

- For each radiation treatment session, the following workflow data (as applicable) will be measured for all patients: 1) total treatment time, 2) average patient movement (VisionRT), and 3) number of beam turn offs due to movement beyond threshold (VisionRT).

5.2.4 Weekly (starting Day 1 +/- 5 days)

- Patient/family-reported health quality of life (QOL), assessed using PedsQL 3.0 Cancer Module, and patient/family-reported anxiety, measured by the modified Yale Preoperative Anxiety Survey Short Form (mYPAS-SF), will be assessed once a week during standard of care weekly on treat visit. The PedsQL for the patient will be optional.

5.3 Follow-up Procedures

Subject will be followed up **30 days (+/- 14 days) after treatment termination** for:

- History & physical exam, vital signs
- Patient/family-reported health quality of life (QOL), assessed using PedsQL 3.0 Cancer Module, and patient/family-reported anxiety, measured by the modified Yale Preoperative Anxiety Survey Short Form (mYPAS-SF). The PedsQL for the patient will be optional.

5.4 Time and Events Table

| PROMISE | Pre-study | Daily For Each Radiation Treatment Session | Weekly During Radiation Treatment³ | Follow-up (30 days +/- 14 days) |
|---------------------------------|------------------|---|--|--|
| Procedures | | | | |
| Informed Consent | X | | | |
| History and PE | X | | | X |
| Performance Status | X | | | X |
| QOL Questionnaires ¹ | X | | X | X |
| Workflow data ² | | X | | |

1: Patient/family-reported health quality of life (QOL), assessed using PedsQL 3.0 Cancer Module, and patient/family-reported anxiety, measured by the modified Yale Preoperative Anxiety Survey Short Form (mYPAS-SF). The PedsQL for the patient will be optional.

2: Workflow data to be measured: 1) treatment time, 2) average patient movement (magnitude, vertical, longitudinal, lateral, yaw, roll, and pitch), and 3) the number beam turn offs due to movement beyond threshold and total time out of tolerance.

3: During standard of care weekly on treat visits QOL questionnaires were be administered. This will not result in additional visits for the patient or family.

5.5 Removal of Subjects from Study

Subjects can be taken off the study treatment and/or study at any time at their own request, or they may be withdrawn at the discretion of the investigator for safety, behavioral or administrative reasons. The reason(s) for discontinuation will be documented and may include:

- 5.5.1 Subject's parent or guardian voluntarily withdraws subject from treatment (follow-up permitted);
- 5.5.2 Subject's parent or guardian withdraws consent (termination of treatment and follow-up);
- 5.5.3 Subject is unable to comply with protocol requirements;
- 5.5.4 Subject demonstrates disease progression (unless continued treatment with study drug/treatment is deemed appropriate at the discretion of the investigator);
- 5.5.5 Subject experiences toxicity that makes continuation in the protocol unsafe;
- 5.5.6 Treating physician judges continuation on the study would not be in the subject's best interest;
- 5.5.7 Development of second malignancy (except for basal cell carcinoma or squamous cell carcinoma of the skin) that requires treatment, which would interfere with this study;
- 5.5.8 Lost to follow-up: If a research subject cannot be located to document survival after a period of 30 days, the subject may be considered "lost to follow-up." All attempts to contact the subject during the 30 days must be documented.

6.0 MEASUREMENT OF EFFECT

Because PROMISE is not a treatment, it will have no direct impact on cancer progression or remission, but its effects on other aspects of treatment and patient quality of life will be measured as discussed in section 2.3.

7.0 ADVERSE EVENTS**7.1 Experimental Therapy**

No experimental therapy (standard of care radiation treatment is used)

7.2 Adverse Event Monitoring

Adverse event data collection and reporting, which are required as part of every clinical trial, are done to ensure the safety of subjects enrolled in the studies as well as those who will enroll in future studies. Adverse events are reported in a routine manner at scheduled times during a trial. Additionally, certain adverse events must be reported in an expedited manner to allow for optimal monitoring of subject safety and care.

All subjects experiencing an adverse event, regardless of its relationship to study therapy, will be monitored until:

- the adverse event resolves or the symptoms or signs that constitute the adverse event return to baseline or is stable in the opinion of the investigator;
- there is a satisfactory explanation other than the study therapy for the changes observed; or
- death.

7.2.1 Definitions

An adverse event is defined as any untoward or unfavorable medical occurrence in a human research study participant, including any abnormal sign (for example, abnormal physical exam, imaging finding or clinically significant laboratory finding), symptom, clinical event, or disease, temporarily associated with the subject's participation in the research, whether or not it is considered related to the subject's participation in the research.

Adverse events encompass clinical, physical and psychological harms. Adverse events occur most commonly in the context of biomedical research, although on occasion, they can occur in the context of social and behavioral research. Adverse events may be expected or unexpected.

Acute Adverse Events

Adverse events occurring in the time period from the signing of the informed consent, through the end of radiation treatment will be considered acute adverse events. These events will not be captured.

Late Adverse Events

Adverse events occurring up to 30 days (+/- 14 days) after the acute adverse event period will be considered late adverse events. These events will not be captured.

Severity

Adverse events will be graded by a numerical score according to the defined NCI Common Terminology Criteria for Adverse Events (NCI CTCAE) Version 5.0. Adverse events not specifically defined in the NCI CTCAE will be scored on the Adverse Event log according to the general guidelines provided by the NCI CTCAE and as outlined below.

- Grade 1: Mild
- Grade 2: Moderate
- Grade 3: Severe or medically significant but not immediately life threatening
- Grade 4: Life threatening consequences
- Grade 5: Death related to the adverse event

Serious Adverse Events

ICH Guideline E2A and the UTSW IRB define serious adverse events as those events, occurring at any dose, which meets any of the following criteria:

- Results in death
- Immediately life-threatening
- Results in inpatient hospitalization^{1,2} or prolongation of existing hospitalization
- Results in persistent or significant disability/incapacity
- Results in a congenital anomaly/birth defect
- Based upon appropriate medical judgment, may jeopardize the subject's health and may require medical or surgical intervention to prevent one of the other outcomes listed in this definition.

Note: A “Serious adverse event” is by definition an event that meets **any** of the above criteria. Serious adverse events may or may not be related to the research project. A serious adverse event determination does not require the event to be related to the research. That is, both events completely unrelated to the condition under study and events that are expected in the context of the condition under study may be serious adverse events, independent of relatedness to the study itself. As examples, a car accident requiring ≥ 24 hour inpatient admission to the hospital would be a serious adverse event for any research participant; likewise, in a study investigating end-stage cancer care, any hospitalization or death which occurs during the protocol-specified period of monitoring for adverse and serious adverse events would be a serious adverse event, even if the event observed is a primary clinical endpoint of the study.

¹Pre-planned hospitalizations or elective surgeries are not considered SAEs.

Note: If events occur during a pre-planned hospitalization or surgery, that prolong the existing hospitalization, those events should be evaluated and/or reported as SAEs.

² NCI defines hospitalization for expedited AE reporting purposes as an inpatient hospital stay equal to or greater than 24 hours. Hospitalization is used as an indicator of the seriousness of the adverse event and should only be used for situations where the AE truly fits this definition and NOT for hospitalizations associated with less serious events. For example: a hospital visit where a patient is admitted for observation or minor treatment (e.g. hydration) and released in less than 24 hours. Furthermore, hospitalization for pharmacokinetic sampling is not an AE and therefore is not to be reported either as a routine AE or in an expedited report.

7.2.2 Unanticipated Problems Involving Risks to Subjects or Others (UPIRSOs):

The phrase “unanticipated problems involving risks to subjects or others” is found, but not defined in the HHS regulations at 45 CFR 46, and the FDA regulations at 21 CFR 56.108(b)(1) and 21 CFR 312.66. For device studies, part 812 uses the term unanticipated adverse device effect, which is defined in 21 CFR 812.3(s). Guidance from the regulatory agencies considers unanticipated problems to include any incident, experience, or outcome that meets ALL three (3) of the following criteria:

- Unexpected in terms of nature, severity or frequency given (a) the research procedures that are described in the protocol-related documents, such as the IRB-approved research protocol and informed consent document; and (b) the characteristics of the subject population being studied;
- AND**
- Related or possibly related to participation in the research (possibly related means there is a reasonable possibility that the incident, experience, or outcome may have been caused by the procedures involved in the research);
- AND**
- Suggests that the research places subjects or others at greater risk of harm (including physical, psychological, economic, or social harm) than was previously known or recognized. Note: According to OHRP, if the adverse event is serious, it would always suggest a greater risk of harm.

Follow-up

All adverse events will be followed up according to good medical practices.

7.3 Steps to Determine If a Serious Adverse Event Requires Expedited Reporting to the SCCC DSMC and/or HRPP

Step 1: Identify the type of adverse event using the NCI Common Terminology Criteria for Adverse Events (CTCAE v5).

Step 2: Grade the adverse event using the NCI CTCAE v5.

Step 3: Determine whether the adverse event is related to the protocol therapy. Attribution categories are as follows:

- Definite – The AE *is clearly related* to the study treatment.
- Probable – The AE *is likely related* to the study treatment.
- Possible – The AE *may be related* to the study treatment.
- Unlikely – The AE *may NOT be related* to the study treatment.
- Unrelated – The AE *is clearly NOT related* to the study treatment.

Note: This includes all events that occur during the acute adverse event period, as defined in section 7.2.1, and is attributed (possibly, probably, or definitely) to the use of PROMISE. Any event that occurs during the late adverse event period and is attributed (possibly, probably, or definitely) to the use of PROMISE must also be reported as indicated in the sections below.

Step 4: Determine the prior experience of the adverse event. Expected events are those that have been previously identified as resulting from administration of the treatment. An adverse event is considered unexpected, for expedited reporting purposes only, when either the type of event or the severity of the event is not listed in:

- the current known adverse events listed in the Agent Information Section of this protocol (if applicable);
- the drug package insert (if applicable);
- the current Investigator's Brochure (if applicable)
- the Study Agent(s)/Therapy(ies) Background and Associated Known Toxicities section of this protocol

7.3.1 Reporting SAEs and UPIRSOs to the Simmons Comprehensive Cancer Center (SCCC) Data Safety Monitoring Committee (DSMC)

All SAE/UPIRSOs at all sites, which occur in research subjects on protocols for which the SCCC is the DSMC of record require reporting to the DSMC regardless of whether IRB reporting is required. All SAEs/UPIRSOs occurring during the protocol-specified monitoring period should be submitted to the SCCC DSMC within 5 business days of the PI or delegated study team members awareness of the event(s). In addition, for participating centers other than UTSW, local IRB guidance should be followed for local reporting of serious adverse events.

The UTSW study team is responsible for submitting SAEs/UPIRSOs to the SCCC DSMC Coordinator. Hardcopies or electronic versions of the eIRB Reportable Event report; FDA Form #3500A forms, or other sponsor forms, if applicable; and/or any other supporting documentation available should be submitted to the DSMC Coordinator. The DSMC Coordinator forwards the information onto the DSMC Chairman who determines if immediate action is required. Follow-up eIRB reports, and all subsequent SAE/UPIRSO documentation that is available are also submitted to the DSMC Chair who determines if further action is required. (See

Appendix III of the SCCC DSMC Plan for a template Serious Adverse Event Form which may be utilized when a sponsor form is unavailable and SAE submission to the eIRB is not required).

If the event occurs on a multi-institutional clinical trial coordinated by the UTSW Simmons Comprehensive Cancer Center, the DOT Manager or lead coordinator ensures that all participating sites are notified of the event and resulting action, according to FDA guidance for expedited reporting. DSMC Chairperson reviews all SAEs/UPIRSOs upon receipt from the DSMC Coordinator. The DSMC Chairperson determines whether action is required and either takes action immediately, convenes a special DSMC session (physical or electronic), or defers the action until a regularly scheduled DSMC meeting.

| |
|--|
| 
Telephone reports to: [name], Clinical Research Manager [contact]
 |

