| RECIST | Response Evaluation Criteria in Solid Tumors |
| SAE | Serious Adverse Event |
| SAbr | Stereotactic ablative body radiotherapy |
| SBRT | Stereotactic body radiotherapy |
| SCCC | Simmons Comprehensive Cancer Center |
| scRNAseq | Single cell RNA sequencing |
| SGOT | Serum Glutamic Oxaloacetic Transaminase |
| SPGT | Serum Glutamic Pyruvic Transaminase |
| TRUS | Transrectal ultrasound |
| WBC | White Blood Cells |

STUDY SCHEMA**Primary Endpoint & Hypothesis**

- Percentage of Children Ages 3-7 Requiring General Anesthesia: We hypothesize that PROMISE will lead to a reduction in the percentage of patients **ages 3-7** who require general anesthesia during radiation treatment from **70%** (institutional historical control) to **30%**.

Secondary Endpoints

Secondary endpoints will be analyzed for those on trial treated with PROMISE vs. anesthesia.

- Patient/family-reported health quality of life (PedsQL 3.0 Cancer Module) and anxiety (mYPAS-SF).
- Workflow data: treatment time, average patient movement, and number of beam turn offs due to movement beyond threshold.
- Overall cost of treatment.

STUDY SUMMARY

| | |
|--|--|
| Title | Pediatric Radiation Oncology with Movie Induced Sedation Effect (PROMISE): A Phase II Clinical Trial to Safely Reduce Anesthesia Use |
| Short Title | PROMISE Clinical Trial to Reduce Anesthesia Use |
| Protocol Number | STU-2021-1005 |
| Phase | Phase II |
| Methodology | Single-arm, open label |
| Study Duration | 2 years |
| Study Center(s) | Single-center |
| Objectives | 
Primary: To decrease the total number of pediatric patients who require general anesthesia through the use of PROMISE.
 
Secondary:
 
 - To assess the impact that PROMISE has on patient/family anxiety and quality of life, treatment time and clinical efficiency, and overall cost. - To determine the average patient movement and beam stoppages with the use of PROMISE. |
| Number of Subjects | 30 |
| Diagnosis and Main Inclusion Criteria | Age 3-11 and planned to undergo radiation therapy. |
| Study Product(s), Dose, Route, Regimen | PROMISE: an audio/visual technology for children to focus on during each radiation treatment to prevent movement. |
| Duration of administration | PROMISE will be used for each fraction of radiation treatment; number of fractions will vary by patient depending on individual diagnosis and treatment plan. |

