Events NOT meeting UPIRSO criteria:

Events that do NOT meet UPIRSO criteria should be tracked, evaluated, summarized, and submitted to the UTSW HRPP/IRB at continuing review.

For more information on UTSW HRPP/IRB reportable event policy, see <https://www.utsouthwestern.edu/research/research-administration/irb/assets/policies-combined.pdf>.

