10.4 Data Management and Monitoring/Auditing

REDCap is the UTSW SCCC institutional choice for the electronic data capture of case report forms for SCCC Investigator Initiated Trials. REDCap will be used for electronic case report forms in accordance with Simmons Comprehensive Cancer Center requirements, as appropriate for the project

The UTSW Simmons Comprehensive Cancer Center (SCCC) Data Safety Monitoring Committee (DSMC) is responsible for monitoring data quality and patient safety for all UTSW SCCC clinical trials. As part of that responsibility, the DSMC reviews all local serious adverse events and UPIRSOs in real time as they are reported and reviews adverse events on a quarterly basis. The quality assurance activity for the Clinical Research Office provides for periodic auditing of clinical research documents to ensure data integrity and regulatory compliance. A copy of the DSMC plan is available upon request.

Trial monitoring will be conducted according to the study specific monitoring plan. For guidance on creating a monitoring plan, refer to the UTSW SCCC IIT Management Manual.

The SCCC DSMC meets quarterly and conducts annual comprehensive reviews of ongoing clinical trials, for which it serves as the DSMC of record. The QAC works as part of the DSMC to conduct regular audits based on the level of risk. Audit findings are reviewed at the next available DSMC meeting. In this way, frequency of DSMC monitoring is dependent upon the level of risk. Risk level is determined by the DSMC Chairman and a number of factors such as the phase of the study; the type of investigational agent, device or intervention being studied; and monitoring required to ensure the safety of study subjects based on the associated risks of the study. Protocol-specific DSMC plans must be consistent with these principles.

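### Section 7.2.1 excludes all acute and late adverse events from capture, contradicting the plan's own grading, logging, reporting and review requirements

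*Combined protocol and SAP*

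**What the plan says.** Section 7.2.1 divides time on study into two adverse event periods. Events from consent to the end of radiation "will be considered acute adverse events. These events will not be captured". Events in the 30 days (+/- 14 days) after that "will be considered late adverse events. These events will not be captured". Neither sentence carries a qualification.

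The surrounding text assumes that events are recorded:

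- **7.2** calls for routine reporting at scheduled times, and for follow-up of every child with an event whatever its cause.
- **7.2.1, Severity:** "Adverse events will be graded by a numerical score according to the defined NCI Common Terminology Criteria for Adverse Events". Events that the dictionary does not define "will be scored on the Adverse Event log according to the general guidelines provided by the NCI CTCAE".
- **7.3, note to Step 3**, on events attributed to PROMISE: "This includes all events that occur during the acute adverse event period, as defined in section 7.2.1". The same note covers attributed events in the late period.
- **7.3.1** sends serious adverse events (SAEs) and unanticipated problems (UPIRSOs) to the data safety monitoring committee in 5 business days.
- **The paragraph on events not meeting UPIRSO criteria** says they "should be tracked, evaluated, summarized, and submitted to the UTSW HRPP/IRB at continuing review".
- **10.4** says the committee "reviews adverse events on a quarterly basis".

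The endpoints in 2.3 include no adverse event measure, table 5.4 has no adverse event row, and 9.3 describes no safety summary. The title is "A Phase II Clinical Trial to Safely Reduce Anesthesia Use".

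**The concern.** The sentences in 7.2.1 are the only place where this protocol defines its adverse event periods, and both periods are marked as not captured. A coordinator who follows them keeps no log. A coordinator who follows 7.3 or the continuing-review paragraph must keep one. Section 10.5 requires the study to be run as written, so each course departs from some part of the protocol.

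Two things are at stake. The first is oversight: the committee and the IRB expect summaries whose source records 7.2.1 says will not exist. The second is the claim in the title. Section 1.2 argues from anesthesia harms, citing motor imbalance in 31% and gastrointestinal effects in 23% of patients after a single episode. Most such events would not be serious, and the 7.3 note covers only events attributed to PROMISE. The plan therefore has no adverse event record of the harms it aims to reduce, and no dependable record of non-serious events related to PROMISE.

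**Working it through.** No figure in the plan bears on this point, so the check is a comparison of texts.

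**1. What the exclusion covers.** The acute period runs from consent to the end of radiation. The late period runs to 30 +/- 14 days after that, that is, to between 30 - 14 = 16 and 30 + 14 = 44 days. Section 4.5 sets the only follow-up visit in the same window after treatment ends. The two periods together therefore cover everything from consent to the last visit.

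**2. Whether an exception is stated.** None is. The sentences do not separate serious from non-serious events, or PROMISE-related events from effects of cancer therapy.

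**3. Each requirement against the exclusion.**

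| Section | What it requires | Can it be met under 7.2.1 as written? |
|---|---|---|
| 7.2 | Routine reporting; follow-up of all events | No |
| 7.2.1, Severity | CTCAE grade; entry on a log | No |
| 7.3, Step 3 note | Attributed events in both periods enter the reporting steps | Only if 7.3 overrides 7.2.1, which is not stated |
| 7.3.1 | SAEs and UPIRSOs to the committee | Only on the same unstated override |
| Non-UPIRSO paragraph | Track and summarize for continuing review | No |
| 10.4 | Quarterly committee review of events | No source data |

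Section 7.3 takes its acute period from 7.2.1, so it requires reporting in the very window that 7.2.1 closes. Section 7.3.1 refers to a protocol-specified monitoring period, and the only such periods in the text checked are the two marked as not captured. The steps in 7.3 also begin by identifying, grading and attributing an event, which presupposes that it has been noted.

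**4. Whether another part of the plan fills the gap.** In part. Section 5.2.3 records movement and beam turn-offs at each session, and footnote 2 of table 5.4 adds total time out of tolerance. These bear on the one PROMISE hazard named in 4.2, movement while the beam is on. They are process measures and do not count harms. No section plans a tabulation of adverse events.

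**The case against.** The best defense is that 7.2.1 is careless wording around a reasonable intention. The intervention is a movie system with no known or expected toxicity (4.2), radiation is standard of care (7.1), and logging every effect of cancer treatment in these children would add work and little information. On this reading, *not captured* means no routine entry of unrelated, non-serious events, with 7.3 left to govern the rest. That would be a sound choice, and the fix below adopts it. But the text does not say it, and even this reading does not fit follow-up of all events in 7.2, the log in 7.2.1 or the continuing-review paragraph.

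A second objection is that 10.4 describes the committee's role for all of the center's trials. That is fair, and it makes 10.4 the weakest of the conflicting passages. The conflict is complete without it.

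A third is that a reader might infer that the trial would yield no safety data at all. The documents do not support that:

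- Reporting of SAEs, UPIRSOs and events attributed to PROMISE remains in the plan, and a UPIRSO need not be a serious event.
- Movement, beam turn-offs and time out of tolerance are recorded.
- General anesthesia status must be known for each child to apply 2.3.1.
- The PedsQL and mYPAS-SF are collected at baseline, weekly and at follow-up, and cover nausea, pain, anxiety and cognitive problems.

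This objection stands against the stronger claim. It does not remove the contradiction, and none of these sources gives an adverse event rate.

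Part of the reporting text, between 7.3.1 and the non-UPIRSO paragraph, and the separate study monitoring plan were not available for this check. They might add reporting rules, but they would not change the two sentences in 7.2.1.

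**Conclusion.** The point holds as an internal contradiction. Two unqualified sentences exclude adverse events for the whole of each child's time on study, and at least five other places require such events to be graded, logged, followed, reported or summarized. The text is wrong as written, and the correction is not a matter of preference.

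The consequence is limited. What would be lacking is systematic recording of non-serious related events, including those of anesthesia, and with it any adverse event rate to support *safely* in the title. It does not follow that nothing would be reported, or that a serious event would necessarily be missed.

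No numerical size is attached. An upper bound based on zero observed events would describe data that do not exist. It would also count all 30 children and all their fractions as treated with PROMISE, although the plan itself expects 30% of those aged 3-7 to need general anesthesia.

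The conclusion assumes that no text outside the copy checked qualifies the two sentences.

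**What to change.** Replace both sentences in 7.2.1 with one limited rule that agrees with 7.3. From consent to the 30-day visit, record on the adverse event log all SAEs and UPIRSOs, and all events judged possibly, probably or definitely related to PROMISE, each with grade and attribution. State explicitly that unrelated, non-serious events of cancer therapy are not recorded. Make 7.2, the continuing-review paragraph and 10.4 refer to this same set of events.

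Add an adverse event row to table 5.4. Add to 9.3 a descriptive safety table giving the number of children with events, and the number of events, by grade and attribution, shown with beam turn-offs and total time out of tolerance.

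Recording anesthesia-related events and mid-course conversions to general anesthesia on the same form would be a useful, cheap addition. It is not needed to resolve the contradiction. Without it, however, the trial could describe PROMISE-related events but would still have no record of non-serious anesthesia events.

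The cost is a protocol amendment, one short form and a small data-entry burden. Sample size, the primary analysis and patient care are unaffected.
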